### 12.4.6 Supplementary analysis

A supplementary analysis of primary efficacy variable 1 will be based on the following estimand:

- Population: Defined through appropriate inclusion/exclusion criteria to reflect the targeted population
- Variable: Percent change from baseline in LDL-C [The primary analysis time point is at Day 330.]
- Treatment: "Inclisiran first" implementation strategy or usual care
- Remaining intercurrent events: 1. Potential use of inclisiran by participants in the usual care group. 2. Discontinuation of study treatment. Data after the occurrence of either one of the above two intercurrent events will be excluded from the analysis (using MMRM).
- Summary measure: Least-squares mean difference between "inclisiran first" implementation strategy and usual care

Subgroup analyses of the two primary efficacy variables will be performed by background lipid-lowering therapy at baseline. Other subgroups to be considered will be defined in the Statistical Analysis Plan.

#### **12.4.7 Supportive analyses**

The primary analysis of the two primary efficacy variables will be repeated for the Per-Protocol Set, Restricted Set 1, and Restricted Set 2.

### **12.5 Analysis supporting secondary objectives**

#### **12.5.1 Efficacy and/or Pharmacodynamic endpoint(s)**

The secondary efficacy variables are the following:

1. Absolute change from baseline in LDL-C
2. Average percent change from baseline in LDL-C levels to each post-baseline visit
3. Average absolute change from baseline in LDL-C levels to each post-baseline visit
4. Achieving  $\geq 50\%$  reduction from baseline in LDL-C (yes, no)
5. Achieving LDL-C  $< 100$  mg/dL (yes, no) (among the subset of participants with LDL-C  $\geq 100$  mg/dL at baseline)
6. Achieving LDL-C  $< 70$  mg/dL (yes, no)
7. Achieving LDL-C  $< 55$  mg/dL (yes, no)
8. Percent change from baseline in apoB
9. Absolute change from baseline in apoB
10. Percent change from baseline in non-HDL-C
11. Absolute change from baseline in non-HDL-C
12. Percent change from baseline in VLDL-C
13. Absolute change from baseline in VLDL-C
14. Percent change from baseline in total cholesterol
15. Absolute change from baseline in total cholesterol
16. Percent change from baseline in Lp(a)

17. Absolute change from baseline in Lp(a)
18. Percent change from baseline in HDL-C
19. Absolute change from baseline in HDL-C
20. Percent change from baseline in triglycerides
21. Absolute change from baseline in triglycerides
22. Intensity of lipid-lowering therapy (decrease in dose, no change in dose, increase in dose)
23. Proportion of days covered (total number of days on either statin, ezetimibe, bempedoic acid or PCSK9 inhibiting monoclonal antibody therapies prescribed divided by total number of study days)

Analyses of secondary efficacy variables 1 and 8 - 21 will be similar to the primary analysis of primary efficacy variable 1 (using MMRM, but with a two-sided 95% confidence interval for the treatment difference).

Secondary efficacy variable 2, 3, and 23 will be analyzed using a linear model with treatment, baseline LDL-C, and [REDACTED] as explanatory variables. Least-squares mean of each treatment group, least-squares mean treatment difference, 95% confidence interval for the treatment difference, and p-value based on the fitted model will be reported.

Secondary efficacy variables 4 - 7 will be analyzed at each post-baseline visit using a logistic regression model with treatment, baseline LDL-C, and [REDACTED] as explanatory variables (Stokes et al 2012). The odds ratio, 95% confidence intervals for the odds ratio, and p-value based on the fitted model will be reported. Missing data will be imputed using “non-responder” (i.e., “negative” outcome) imputation.

Secondary efficacy variable 22 will be analyzed at each post-baseline visit using a proportional odds model with treatment, baseline LDL-C, and [REDACTED] as explanatory variables (Stokes et al 2012). The odds ratios, 95% confidence intervals for the odds ratios, and p-values based on the fitted model will be reported. Missing data will not be imputed.

Visit-to-visit LDL-C variability from Day 90 until Day 330 will be reported, using various measures of variability (standard deviation, coefficient of variation) (Bangalore et al 2015).

Analyses of secondary efficacy variables will be based on the Full Analysis Set.

## 12.5.2 Safety endpoints

For all safety analyses, the Safety Set will be used. All listings and tables will be presented by treatment group.

### Adverse events

All information obtained on adverse events will be displayed by treatment group and participant.

The number (and percentage) of participants with treatment-emergent adverse events (events started after the first dose of study medication or events present prior to start of double-blind

treatment but increased in severity based on preferred term) will be summarized in the following ways:

- by treatment group, primary system organ class and preferred term.
- by treatment group, primary system organ class, preferred term and maximum severity.
- by treatment group, Standardized MedDRA Query (SMQ) and preferred term.

Separate summaries will be provided for study medication related adverse events, death, serious adverse events, other significant adverse events leading to discontinuation.

A participant with multiple adverse events within a primary system organ class is only counted once towards the total of the primary system organ class.

### Vital signs

All vital signs data will be listed by treatment group, participant, and visit/time and if ranges are available, abnormalities will be flagged. Summary statistics will be provided by treatment and visit/time.

### Clinical laboratory evaluations

All laboratory data will be listed by treatment group, participant, and visit/time, and if reference ranges are available, abnormalities will be flagged. Summary statistics will be provided by treatment and visit/time.

#### 12.5.3 Pharmacokinetics

Not applicable.

#### 12.5.4 DNA

Not applicable.

#### 12.5.5 Biomarkers

See [Section 12.5.1](#).

#### 12.5.6 PK/PD relationships

[figure not shown]
Not applicable.

[REDACTED]

[REDACTED]

[REDACTED]

[REDACTED]

## 12.7 Interim analyses

After all participants complete their baseline visit, the demographic and baseline characteristics may be summarized to help design new studies. No analysis will be performed using post-baseline data. Thus, there is no need to adjust the level of significance for such interim analysis of baseline data.

## 12.8 Sample size calculation

### 12.8.1 Primary endpoint(s)

The sample size was calculated for the two primary efficacy variables with adjustment for multiple testing by using the Bonferroni procedure.

For primary efficacy variable 1, i.e., percent change from baseline in LDL-C, the standard deviation is assumed to be 40, partly based on the results from ORION-10 and ORION-11 clinical trials, and considering that the standard deviation will likely be larger in this trial since changes in lipid-lowering therapy are allowed in both treatment groups. An expected mean treatment difference of 15 is assumed, which is smaller than the mean difference observed in the Phase III trials, to account for 1) potential lower utilization of background lipid-lowering therapy in the "inclisiran first" implementation group compared to the usual care group, and 2) the ability to add non-statin lipid lowering therapy (including participants who may have used commercially available inclisiran), in the usual care group.

Table 12-1 considers total sample sizes for expected mean treatment differences of 15, 20, and 25 and powers of 0.85 and 0.90 (nQuery Version 8.4.1.0). From Table 12-1, an expected mean treatment difference of 15 at Day 330 and a power of 0.90 were chosen to provide a total sample size of 354 participants.

**Table 12-1 Sample size calculations for percent change from baseline in LDL-C**

Mean treatment difference	Power = 0.85	Power = 0.90
---------------------------	--------------	--------------

15	306	354
20	172	200
25	112	128

For primary efficacy variable 2, i.e., discontinuation of statin therapy (yes, no), a [REDACTED] for a non-inferiority test of two proportions, an allocation ratio of 1:1, and a one-sided significance level of 0.0125 were used in the calculation of sample size. Table 12-2 considers total sample sizes for 0.20 and 0.25 as the true proportions of participants who discontinue statin therapy in each treatment group, and non-inferiority margins of 0.10 and 0.15 for the "inclisiran first" implementation group to be no worse than the usual care group (nQuery Version 8.4.1.0). From Table 12-2, a true proportion of 0.20 for participants who discontinue statin therapy in each treatment group by Day 330, a non-inferiority margin of 0.15, and a power of 0.90 were chosen to provide a total sample size of 354 participants.

**Table 12-2 Sample size calculations for statin therapy discontinuation**

Proportion in usual care group	Non-inferiority margin	Power = 0.85	Power = 0.90
0.20	0.10	688	796
0.20	0.15	306	354
0.25	0.10	806	932
0.25	0.15	360	414

Based on the sample size calculations in Table 12-1 and Table 12-2, a total sample size of 354 together with a loss to follow-up rate of 10% at Day 330 and a statin intolerance rate at baseline of 10% (i.e., a total of 20% due to loss to follow-up and statin intolerance at baseline) require approximately 444 participants (222 participants per treatment group) to be randomized. This will also allow examination of subgroups with reasonable sample sizes.

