**Duration of study period:** The study is designed as a one-year trial (a total of three inclisiran doses). The Phase III trials of inclisiran had a follow-up duration of 18 months. In the Phase II trial (ORION-1), it was shown that the second dose at Day 90 lowers LDL-C slightly more than after a single administration (Ray et al 2017). Based on these trials, the maximum reduction in LDL-C is achieved approximately 4 to 5 months after initiation of therapy. Prior studies have shown that approximately one-third of patients discontinue statin therapy in the three years following initiation of therapy (Khunti et al 2018). A follow-up duration of one year enables: 1) observation of the steady-state LDL-C lowering effect of inclisiran, 2) observation of a meaningful difference in statin discontinuations, should such a difference exist, and 3) assessment of variables that likely require longer-term treatment to observe meaningful treatment differences, such as patient reported outcomes.

**Choice of non-inferiority margin for discontinuation of statin therapy:** The sample size of the trial, as described in [Section 12.8.1](#), is partially based on the co-primary efficacy variable of discontinuation of statin therapy. The non-inferiority margin of 0.15 in the proportion of participants who discontinue statin therapy by Day 330 was chosen to reflect a clinically meaningful difference in statin discontinuation rates between the groups, while considering statin discontinuation rates described in other studies ([Khunti et al 2018](#)).

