### 12.4.4 Handling of missing values not related to intercurrent event

For the primary analysis of primary efficacy variable 1, the MMRM implicitly imputes missing data under a missing at random assumption.

For the primary analysis of primary efficacy variable 2, participants for whom it cannot be ascertained that they are on statin therapy at the end of study will be assumed to have discontinued statin therapy.

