2.5.1 Primary endpoint(s)

The primary efficacy variables are the following:

1. Percent change from baseline in LDL-C
2. Discontinuation of statin therapy (i.e., no statin use \geq 30 days before the end-of-study visit) (yes, no)

The primary analysis time point for both primary efficacy variables is at Day 330.

The following provides additional details on the derivation of primary efficacy variable 2.

If a participant is considered a study completer and has a non-missing visit date for the nominal Day 330 visit recorded, a statin assessment date (to assess if the participant was taking statins at this point in time) will be calculated by subtracting 30 days from the Day 330 visit date (e.g., study Day 300 if the participant completes on study Day 330). The statin assessment date will be compared to the maximum statin end date of all statin medications taken by the participant. If the last statin is recorded as ongoing at study end date, the maximum statin end date will be set to the study end date.

- If the participant was on a statin on or after this statin assessment day (maximum statin end date \geq statin assessment date), the participant will be considered as discontinued statin = 'no.'
- If the participant was not on a statin on and after this statin assessment day (maximum statin end date $<$ statin assessment date), or they were a completer who did not have a Day 330 visit, the participant will be considered as discontinued statin = 'yes.'

All early termination participants will be considered to not be on a statin for this endpoint (the participant will be considered as discontinued statin = 'yes').

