For primary efficacy variable 2, a one-sided 98.75% confidence interval for treatment difference ("inclisiran first" implementation strategy – usual care) in the proportion of participants who discontinued statin therapy at Day 330 will be computed using the normal approximation to the binomial distribution. Non-inferiority of the "inclisiran first" implementation strategy to usual care will be declared if the upper limit of the confidence interval does not exceed the non-inferiority margin of 0.15. The difference in proportions and associated two-sided 97.5% confidence interval will also be provided.

The primary analysis of primary efficacy variable 2 will be based on the FAS excluding participants who had medical history of statin intolerance. The primary analysis of this variable will be repeated for the Per-Protocol Set and Restricted Set 2.

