2.5.4 Handling of missing values not related to intercurrent event

For the primary analysis of primary efficacy variable 1, the MMRM implicitly imputes missing data under a missing at random assumption.

For the primary analysis of primary efficacy variable 2, participants for whom it cannot be ascertained that they are on statin therapy at the end of study will be assumed to have discontinued statin therapy (discontinued statin = 'yes').

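### The 0.90 power stated for statin-discontinuation non-inferiority belongs to a set without the lost participants, whereas the planned analysis keeps them and counts them as discontinued

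*Protocol*

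**What the plan says.** **Sample size (Protocol 12.8.1; SAP section 3).** For statin discontinuation the plan takes "a true proportion of 0.20 for participants who discontinue statin therapy in each treatment group by Day 330, a non-inferiority margin of 0.15", a one-sided level of 0.0125 and power 0.90, which gives 354 participants. It starts the inflation from "a total sample size of 354 together with a loss to follow-up rate of 10% at Day 330", adds 10% for statin intolerance, and so allows for "a total of 20% due to loss to follow-up and statin intolerance at baseline". The result is about 444 randomised (222 per arm). The percent-change-in-LDL-C calculation also gives 354, so one inflation serves both primary endpoints.

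**Analysis set (SAP 2.5.2).** "The primary analysis of primary efficacy variable 2 will be based on the FAS excluding participants who had medical history of statin intolerance". Nobody is removed for loss to follow-up.

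**Counting rule.** SAP 2.5.1 states: "All early termination participants will be considered to not be on a statin for this endpoint". The same section codes a completer with no Day 330 visit as discontinued. Protocol 12.4.4 says that "participants for whom it cannot be ascertained that they are on statin therapy at the end of study will be assumed to have discontinued", and SAP 2.5.4 repeats the rule.

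Neither sample-size section says whether 0.20 includes the participants whom this rule turns into discontinuations.

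**The concern.** The same participant is treated in two ways. In the sample-size section, a participant who is lost contributes nothing. In the analysis, that participant stays in the denominator and adds an event. Both inputs to the power calculation therefore change: the analysed number rises from 354 to about 400, and the expected proportion may rise above 0.20. These changes pull power in opposite directions, and which one prevails depends on what 0.20 covers.

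At stake is the one power figure that the plan gives for one of its two primary hypotheses. If non-inferiority is not shown, readers will use that figure to judge how informative the result is. As written, they cannot tell whether the planned analysis had more or less than 0.90.

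**Working it through.** **Inputs.** One-sided level 0.0125, margin 0.15, proportion 0.20 in each arm, power 0.90, 1:1 allocation, 10% loss, 10% intolerance and 444 randomised all come from Protocol 12.8.1 and SAP section 3. The analysed set and counting rule come from SAP 2.5.1, 2.5.2 and 2.5.4 and Protocol 12.4.4. Normal quantiles: z(0.9875) = 2.2414, z(0.90) = 1.2816.

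**1. The plan's own figures.**
- n per arm = (2.2414 + 1.2816)² × 2 × 0.20 × 0.80 / 0.15² = 176.5, rounded up to 177, so 354 in total. All eight cells of Table 12-2 reproduce in this way.
- Power at 177 per arm and 0.20 is 0.901.
- 354 / (1 − 0.20) = 442.5, consistent with approximately 444.

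The printed numbers are right for the set that they describe.

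**2. The set that is analysed.** Only the statin-intolerant are removed: 444 × 0.90 = 399.6, or 199.8 per arm.

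**3. The proportion that is counted**, with 10% loss in each arm and every lost participant coded as discontinued:
- *0.20 is the rate among followed participants.* Counted proportion = 0.10 + 0.90 × 0.20 = 0.28.
- *The same, with the 10% loss taken as a share of all randomised and falling on the statin-tolerant.* This is how the plan's additive 10% + 10% reads. Then 44.4 / 399.6 = 11.1% of the analysed set are lost, and the counted proportion = 0.111 + 0.889 × 0.20 = 0.289.
- *0.20 already includes the lost.* Counted proportion = 0.20, which implies a rate among the followed of (0.20 − 0.10) / 0.90 = 0.111.

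**4. Power of the planned rule**, with no true difference: Φ(0.15 / √(2p(1 − p)/199.8) − 2.2414).

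| Meaning of 0.20 | Counted p | Power |
|---|---|---|
| Rate among followed, 10% loss in analysed set | 0.28 | 0.864 |
| Rate among followed, 10% loss of all randomised | 0.289 | 0.857 |
| Already includes the lost | 0.20 | 0.934 |

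Simulating the planned confidence-limit rule with 200 per arm (400,000 trials per scenario) gave 0.865 at 0.28 and 0.934 at 0.20.

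**5. Dependence on loss.** If 0.20 is the rate among the followed:
- 5% loss gives p = 0.05 + 0.95 × 0.20 = 0.24 and power 0.898.
- 15% loss gives p = 0.15 + 0.85 × 0.20 = 0.32 and power 0.835.

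Power is 0.90 when the counted proportion is about 0.2375. Under this reading that is a loss of (0.2375 − 0.20) / 0.80 = 4.7%, below the plan's own 10%.

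**The case against.** The strongest reply is that no false figure has been printed. The 0.90 is a design input used to choose a table cell, and it reproduces. The proportion is stated for each whole treatment group by Day 330, in the same terms as the hypotheses. It can therefore be read as the proportion under test, with the counting rule built in. Applying one combined allowance to both endpoints is then ordinary caution, and power for this endpoint is 0.93, above target. Table 12-2 also shows a row at 0.25, so some sensitivity to the rate is visible. The final result will in any case be judged on its confidence interval, not on planned power.

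Much of this stands. The reading is available, the documents do not exclude it, and it removes any shortfall. But it gives 0.93, not 0.90, so the stated power still does not describe the planned analysis. It also makes the loss allowance unnecessary for this endpoint. The 0.25 row stops short of 0.28 and is not linked to loss; at 0.25 with 199.8 per arm, power is 0.889.

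A reader might try to settle the meaning of 0.20 from Protocol 4.1, which reports that about one-third of patients stop statins over three years. The documents do not support that. The figure concerns patients after statin initiation, whereas participants here are already treated, and the protocol nowhere converts it into 0.20.

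**Conclusion.** The point holds as a minor mismatch between the set that was powered and the set that is analysed. On neither reading of 0.20, at the plan's own 10% loss, is power 0.90. It is about 0.86 (0.857 to 0.864) if 0.20 is the rate among followed participants, and about 0.93 if 0.20 already includes the lost. The first reading fits better with taking the lost off before applying 0.20, but the text does not state it.

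These figures assume equal 10% loss in both arms, that this 10% stands for everyone the rule codes as discontinued, and no true difference. Equal loss matters. As an illustration that is not in the documents, take 0.20 among the followed, with 12% loss under inclisiran first and 8% under usual care. The counted rates are then 0.296 and 0.264, and power is about 0.65; with the losses reversed it is about 0.97.

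A reader might infer that the trial is underpowered and should enrol more. The documents do not support that. Power 0.90 at a counted 0.28 would need 223 per arm, or 446 / 0.90 = about 496 randomised, but only under one of two open readings. Under the other, 354 / 0.90 = about 394 would be enough. The 444 also serves the LDL-C endpoint, where an allowance for loss is appropriate. Type I error, margin and decision rule are untouched.

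**What to change.** In Protocol 12.8.1 and SAP section 3:

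1. State whether 0.20 is the rate among followed participants or already includes those counted as discontinued because they were lost.
2. For statin discontinuation, replace 0.90 with the power for about 400 analysed participants under the lost-equals-discontinued rule.
3. If the meaning of 0.20 cannot be settled, give the range 0.86 to 0.93 with its assumptions: 10% loss in each arm and no true difference.

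Leave the number randomised, margin, missing-data rule and decision rule as they are.

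The cost is one or two sentences in each document. The stated power for this endpoint may become slightly less favourable.

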### 12.8.2 Secondary endpoint(s)

Not applicable.

## 13 Ethical considerations and administrative procedures

### 13.1 Regulatory and ethical compliance

This clinical study was designed and shall be implemented, executed and reported in accordance with the ICH Harmonized Tripartite Guidelines for Good Clinical Practice, with applicable local regulations (including European Directive 2001/20/EC, US CFR 21), and with the ethical principles laid down in the Declaration of Helsinki.

### 13.2 Responsibilities of the investigator and IRB/IEC

Before initiating a trial, the investigator/institution must obtain approval/favorable opinion from the Institutional Review Board/Independent Ethics Committee (IRB/IEC) for the trial protocol, written informed consent form, consent form updates, participant recruitment procedures (e.g.,

advertisements) and any other written information to be provided to participants. Prior to study start, the investigator is required to sign a protocol signature page confirming his/her agreement to conduct the study in accordance with these documents and all of the instructions and procedures found in this protocol and to give access to all relevant data and records to Novartis monitors, auditors, Novartis Quality Assurance representatives, designated agents of Novartis, IRBs/IECs, and regulatory authorities as required. If an inspection of the clinical site is requested by a regulatory authority, the investigator must inform Novartis immediately that this request has been made.

